## 1. Background

Bangladesh is experiencing rapid urbanization, with more than a third of people (~65 million) living in urban areas in 2018; by 2050, this number is projected to increase to 118 million[1]. Despite increasing urbanization, significant gaps remain in nutrition outcomes, determinants, and quality of health services in urban areas, particularly for the poor. Chronic malnutrition (stunting) in urban areas is decreasing at a slower rate than in rural areas [2], with stunting rates remaining as high as 50% in urban slums [3]. Furthermore, health policy heavily focuses on rural delivery of health services and improvements in health and nutrition outcomes for rural residents [4]. Coverage, standardization, and quality of maternal, infant, and young child nutrition (MIYCN) counselling is neglected and weak across health care delivery systems in Bangladesh [5].

To address these gaps, Alive & Thrive (A&T) aims to develop and test effective, feasible, and scalable models for delivering MIYCN counselling in urban areas and evaluate their impact on utilization, knowledge, and behaviors. The Bangladeshi urban MIYCN model is being delivered through NGO platforms that currently provide health services to urban women and children. The intervention includes community mobilization and social and behavior change communication (SBCC) for MIYCN. The package of maternal nutrition interventions is aligned with the latest global evidence [6] and the national policies and guidelines of Bangladesh Government within routine maternal, newborn and child health (MNCH) services. These include building capacity for health providers and nutritional counselors in urban health facilities, creating friendly environment for MIYCN counselling in health facility settings, community mobilization for demand creation of MIYCN services, interpersonal counselling on diet during pregnancy and consumption of iron folic acid (IFA) and calcium, promotion of adequate weight-gain monitoring during pregnancy, and counselling on breastfeeding and complementary feeding practices.

To assess the effectiveness of the interventions, A&T and IFPRI designed a quasi-experimental evaluation study with data collection taking place in three stages: 1) Baseline data collection to assess comparability of facilities, service quality and client's behaviors, 2) Facility-based endline data collection and 3) Community-based endline survey. A&T partnered with 2 NGOs, Radda and Marie Stopes, whose facilities provide MNCH services in urban areas, but not affiliated with the Bangladesh Urban Primary Health Care Services Delivery Project (UPHCSDP). These NGOs each operates 4 facilities in Dhaka (8 in total) which are eligible for the study to form the intervention

group. The evaluation comparison group is a matched sample of 8 facilities operated by NGOs Nari Maitree and Shimantik (NGOs under contract with the UPHCSDP implemented by Government of Bangladesh). The UPHCSDP agreed to provide facilities for baseline and endline data.

## 2. Impact of COVID-19 on program interventions and implementation

In March 2020, the World Health Organization declared COVID-19 a pandemic. Bangladesh reported its first case on March 8, 2020. On March 26, the Government of Bangladesh issued a nationwide extended public holiday and strict stay-at-home order. The initial stay-at-home order remained in place through May 30, after which localized restrictions were enforced.

Disruptions to field conditions and health facility operations resulted in adaptations to program implementation. In-person orientations and trainings to all healthcare providers was no longer possible; instead, A&T began providing virtual orientations to MIYCN Counselors and community workers (CWs) and providing newly recruited counselors and CWs with periodic technical refreshers and peer-to-peer training with trained counselors. Community mobilization, media activities, and other interventions which required in-person gatherings were suspended due to restrictions on social gatherings. In their place, MIYCN flyers promoting health facility counselling services and a script for the provision of MIYCN education and counselling services via phone were developed. Supportive supervision was also conducted via phone. The full description of planned and actual interventions at health facilities are provided in Table 1.

Table 1. Description of interventions and differences between intervention and comparison facilities

CORE INTERVENTIONS	PLANNED INTERVENTION	ACTUAL INTERVENTION	CONTROL
At health facilities:			
Training for health providers and nutritional counselors	In-person training on MIYCN SBCC from A&T, counseling skills training, general SBCC training, and supportive supervision training (managers only).	Only MIYCN Counselors received the full, in-person training. CW training was disrupted by COVID and CWs received basic training only Adapted virtual orientations, trainings, and technical periodic refreshers were provided. High staff turnover. Replacement MIYCN Counselors and CWs received peer-to-peer training with trained counselors.	Standard training on counseling skills, SBCC and supervision, if available
Counseling rooms in health facility settings	Counseling rooms available with standardized layouts, displays of government IYCF logo, and other specifications.	As planned	Non-standardized counseling rooms
SBCC materials and job aids	Availability of standardized MIYCN-specific BCC materials and job aids.	As planned, with the additional development of the mobile MIYCN (m-MIYCN) script and MIYCN flyer.	Standard SBCC materials and job aids if available, but used for mixed purposes
MIYCN counseling services and procedures	Standardized MIYCN counseling services and procedures by a dedicated counselor. MIYCN counseling topics include diet diversity and quantity, IFA and calcium supplementation, weight gain monitoring, exclusive and early initiation of breastfeeding, complementary feeding, and water, sanitation and health.	MIYCN Counselors provide routine MIYCN counseling services during individual appointments. Small group education sessions (with 4-5 women) began at health facilities in July 2021. General counselors provide these services in the absence of the MIYCN Counselor.	Offered only at facilities where a counselor is available
In the community:			
Social mobilization and community events	Mass media campaigns, advocacy meetings, MIYCN fair, film shows, special day/week events (Safe Motherhood Day, National Handwashing Day, National Nutrition Week, World Breastfeeding Week), ANC camps and other community meetings.	Mass media campaigns, advocacy meetings, MIYCN fairs and film shows were permanently suspended. Light community mobilization efforts include satellite clinic outreach (RADDA facilities only) and MIYCN flyer distribution, distribution of MIYCN flyers to community referrers (MSB facilities only), and monthly ANC camps for pregnant women (MSB facilities only).	Standard community events

Home visits	Promote health facility visits, referrals to MIYCN counselors, attendance at special events, and general MIYCN information.	Mobile MIYCN (m-MIYCN) education (provided by CWs) was provided via phone to pregnant women and mothers in place of home visits until November 2020.	Home visits for routine health services
Staff hiring and supervision			
Hire, train, equip and support a dedicated MIYCN counselor and CW at each health facility.	MIYCN Counselors will deliver standardized nutrition interventions and messages as part of MICYN services, maintain client registers for monitoring and reporting, and provide supervision. CWs will identify and mobilize beneficiaries needing services in the community	As planned	No additional staff hiring
Supportive supervision of MIYCN Counselors and CWs	Program Managers, Facility Managers, and Field Supervisors conduct supportive supervision of services provided by MIYCN Counselors and CWs.	Supportive supervision of MIYCN Counselors and CWs was conducted via phone and included listening in on mobile counseling sessions, using a checklist to assess quality of counseling, and providing feedback. In-person supportive supervision resumed in October 2020.	Standard health facility supervision.

### 3. Objectives of study

The primary objectives of the proposed evaluation are to answer the following questions using a quasi-experimental evaluation design:

- Is it **feasible** to standardize the delivery of MIYCN counseling services in existing urban health facilities?
- Can **quality of MIYCN counseling service** be improved by upgrading and standardizing existing MIYCN counseling service in urban health facilities?
- What are the **impacts** of standardized and upgraded MIYCN counseling service **on utilization** of MIYCN services and knowledge of clients?

The secondary objectives are:

- What are the **impacts** of standardized and upgraded MIYCN counseling service on behaviors of clients including:
  - Pregnant women: 1) consumption of diversified foods; 2) intake of IFA and calcium supplements during pregnancy
  - Mothers of children <1 y: age-appropriate infant feeding

### 4. Key study outcomes

The primary outcomes to be evaluated include **quality measures of MIYCN counseling in urban areas**

- Facility readiness for nutrition services, resources, and staffing
- Knowledge of service providers on key nutrition services
- Quality of nutrition counseling during ANC (such as diversified diet during pregnancy, IFA and calcium intake, promotion of maternal weight monitoring and related counseling) and during well-child or sick-child contacts (such as age-appropriate feeding practices, promotion of child growth and related counseling).
- Clients' utilization of and satisfaction with MIYCN services
- Clients' knowledge of MIYCN topics and best practices

The secondary outcomes to be evaluated include **maternal nutrition practices and IYCF practices**

- Maternal dietary diversity

[figure not shown]
- Iron/folic acid supplementation: proportion of women who consumed at least 100 IFA tablets and the mean number of tablets consumed.
- Calcium supplementation: proportion of women who consumed calcium and the mean number of tablets consumed.
- Early initiation of breastfeeding
- An indicator of age-appropriate feeding that includes exclusive breastfeeding for children <6 months, breastfeeding + complementary feeding for children 6-12 months. We consider children < 12 months as they are more likely to be exposed to the program through immunization contacts.

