## 7. Sample size and power calculation

Sample size has been estimated based on the baseline prevalence of the primary outcomes, the expected change after intervention, the power to detect those differences at 0.80, and a level of significance of 0.05. The outcomes used for sample size calculation were quality of nutrition service delivery (including provision of counseling on diet and breastfeeding practices). The sample size was calculated at 2 levels: provision of services (measured through case observation) and receipt of services (measured through client interviews).

Based on data from baseline assessment, we calculated the prevalence for expected outcomes, and the intra-cluster correlations (ICCs). We estimated that a minimum sample size of 1200 clients per group during the first phase of the endline survey conducted at the facilities would have at least 80 percent power to detect a difference of 10-19 percentage points (pp) between intervention and comparison groups in the changes over time for different context-specific outcomes (**Table 2**), e.g. maternal counselling during pregnancy and IYCF counselling to caregivers of young children. During the follow up in the communities, we expect a ~30-33% loss from the original sample, and thus estimate we will collect information from 65-70%. We expect that this will give us enough power to detect changes in context-specific behavioral outcomes. Instead of separating the sample for ANC and child contacts, we will pool them to examine context-appropriate behavior such as pregnant women with dietary diversity/IFA and calcium consumption and caregivers with age-appropriate child feedings. These detectable differences are of reasonable public health significance and based on the previous experience from evaluation of the A&T Bangladesh maternal nutrition study [7].

For facility readiness and provider knowledge, with the sample size of 8 facilities and 40-64 providers in this group, we will mainly report the descriptive analyses between two groups, but not report statistical test due to small sample size.

Table 2. Sample size and power calculation

	Control group, endline 	Expected difference	Treatment group, endline	Power	ICC	Alpha	Sample size per group
Quality of services (measured through case observation)							1200
Counseling on diet	68.0	19.0	87.0	0.8	0.103	5	
Counseling on breastfeeding	71.6	17.1	88.7	0.8	0.09	5	

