Context-appropriate behavioral outcomes (measured through client interview)							1200 at facility-based endline 800 (67%) at community-based endline
Consume 100+ IFA	54.5	9.5	64.0	0.8	0.001	5	
Dietary diversity during pregnancy	74.0	9.5	83.5	0.8	0.009	5	
Early initiation of breastfeeding	32.8	13.5	46.3	0.8	0.024	5	

Data from AINNS study [8]

Data from Bangladesh DHS 2014 [9]

We expect to see no difference in the control group at baseline vs. endline.

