- Pregnant women who are visiting the health facilities for ANC visits (at least twice during her pregnancy, around half of clients)
- Mothers with children <12 months of age who are visiting the health facilities for health check-ups or vaccination

Exclusion criteria:

- Pregnant women with severe illness or complications
- Mothers with severely ill children

For the assessment of **impacts** of standardized and upgraded MIYCN counseling service on coverage and behavior changes we will identify each facility's catchment area and find women in the community who accessed services at those health facilities to sample 1600 facility clients (PW and RDW) to interview (**Table 4**). During the facility interviews, we will seek their consent to be interviewed at home for the community

interview at a later time. Follow-up with clients for the community interview was conducted within 3 months following the facility interview at baseline. At endline, facility clients will be visited within one month to conduct the community interview. We expect that we will be able to follow 65-70% of these women. By doing so, we ensure that our clients will have at least one visit in the evaluation facilities (both intervention and control areas). We can track the number of clinic visits and thus conduct the dose response analysis.

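### 100+ IFA and the mean IFA and calcium counts are cut off at the interview in ongoing pregnancies, and the analysis plan has no gestational-age term

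*Combined protocol and SAP*

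**What the plan says.** - **Outcomes.** Section 4 lists, as secondary outcomes, the "proportion of women who consumed at least 100 IFA tablets and the mean number of tablets consumed", the proportion taking any calcium, and the mean calcium count.
- **Who is asked, and about what.** Section 3 lists "intake of IFA and calcium supplements during pregnancy" under pregnant women. Section 7 describes the pooled behavioural outcome as "pregnant women with dietary diversity/IFA and calcium consumption and caregivers with age-appropriate child feedings". Table 7, module 3 (section 9.4) asks pregnant women about consumption in the current pregnancy.
- **Recruitment.** The criterion in section 8 is "Pregnant women who are visiting the health facilities for ANC visits (at least twice during her pregnancy, around half of clients"). It sets no minimum or maximum gestation.
- **Timing.** Section 9 measures behaviour at the home interview. Section 8 says "Follow-up with clients for the community interview was conducted within 3 months following the facility interview at baseline"; at endline the limit is one month.
- **Analysis.** Section 10 specifies ANCOVA with facility random effects. It names no covariate and does not define the baseline term. Section 7 describes the target difference as one "between intervention and comparison groups in the changes over time for different context-specific outcomes".
- **Numbers.** Table 2 gives 100+ IFA as 54.5% versus 64.0%, ICC 0.001, power 0.8, under a block headed "800 (67%) at community-based endline". Section 8 plans to "sample 1600 facility clients (PW and RDW) to interview". Table 4 plans 400 ANC and 400 child-contact client interviews per group at endline.

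**The concern.** A tablet count in an ongoing pregnancy grows with each week. Two women with the same start and the same adherence fall on opposite sides of 100 tablets if one is interviewed early and the other late. With one tablet a day from week 16 (an assumption for arithmetic only), 100 tablets cannot be reached before week 16 + 100/7 = 30.3.

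This matters here because the arms are run by different NGOs and are not randomised. If intervention women attend ANC earlier, an effect is masked; if later, an effect is mimicked. Table 1 describes community workers who mobilise clients and, at one NGO's facilities, monthly ANC camps. Such activities could change the timing of attendance in one arm and only by endline. The shorter home-visit lag at endline also shifts gestation at interview, and the share already delivered, between rounds.

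The any-calcium proportion is less sensitive to gestation. The primary outcomes are not affected.

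**Working it through.** **1. The plan's own power figure for 100+ IFA.** Inputs from Table 2: p1 = 0.545, p2 = 0.640, ICC = 0.001; 8 facilities per group; two-sided 0.05 (sidedness is assumed). Formula: power = Φ{[0.095·√(n/DE) − 1.96·√(2p̄(1−p̄))] / √(p1(1−p1) + p2(1−p2))}, with DE = 1 + (m−1)·ICC and p̄ = 0.5925. The two roots are 0.6949 and 0.6917.

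- n = 800, m = 100: DE = 1.099, n/DE = 727.9, z = (2.563 − 1.362)/0.6917 = 1.737, power 0.96.
- n = 400, m = 50: DE = 1.049, n/DE = 381.3, z = (1.855 − 1.362)/0.6917 = 0.713, power 0.76. About 440 per group are needed for 0.80.

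The stated 0.8 is not reproduced exactly at either size. It is exceeded at 800 and missed at 400. The same formula gives about 1,220 and 1,214 per group for the two counselling rows, close to the plan's 1200.

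**2. Sensitivity of the outcomes to gestation (illustration).** Assumptions, none from the documents: gestation at interview uniform from week a to 40; supplements started uniformly over weeks 12–20; tablets on 50–100% of days; no treatment effect. Count = 7 × (gestation − start) × share of days, floored at zero. One arm is shifted one week earlier.

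| a | 100+ share | one week earlier | change (points) | change in mean count | weeks equal to 9.5 points |
|---|---|---|---|---|---|
| 12 | 16.9% | 14.2% | 2.8 | 4.4 | 3.4 |
| 20 | 23.7% | 19.8% | 3.8 | 5.2 | 2.5 |
| 28 | 39.4% | 33.1% | 6.3 | 5.3 | 1.5 |

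These shares lie below Table 2's 54.5%. Moving the start weeks until 54.5% reach 100 gives 3.6 to 8.3 points per week, but some of those scenarios need implausibly early starts (weeks 1–9). A different set of assumptions (mean gestation 26–32 weeks, SD 6; mean start week 14–20, SD 3; 0.7–0.9 tablets a day) gives 0.7 to 5.1 points per week. The sign always follows the sign of the gestational difference.

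**3. Precision.** In the table's scenarios gestation explains 45%, 40% and 25% of the variance of the 100+ indicator, and 84%, 70% and 40% of that of the count.

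**4. What baseline adjustment removes.** A difference that is stable over time cancels in a change-over-time analysis; one that is new at endline does not. For ANCOVA, assume the covariate is the facility baseline mean and facility effects are stable. With 50 women per facility in intervention (400/8) and 8.75 in comparison (70/8), the slope is 2·ICC/[V(50) + V(8.75)], where V(n) = ICC + (1−ICC)/n. It removes about 1.5% of a stable difference at ICC 0.001, 12% at 0.009, 27% at 0.024 (Table 2's behavioural ICCs) and 44% at 0.05.

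**5. What the baseline balance check could see.** Half-width of the 95% interval for a gestational difference, 400 versus 70 ANC interviews, before clustering: 1.96 × (40−a)/√12 × √(1/400 + 1/70) = 2.1, 1.5 and 0.9 weeks for a = 12, 20 and 28.

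**6. Delivered by the endline home interview.** With lag uniform over 0–30 days and birth at week 40: 8%, 11% and 18%.

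**The case against.** The strongest reply is that no imbalance is shown. The documents give no gestational-age distribution, section 1 calls the comparison facilities a matched sample, and section 10 plans a baseline balance check. This stands as to size and sign: neither can be stated. It does not remove the exposure, because matching on gestation is not mentioned and the check is imprecise (step 5).

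A reader might go further in several ways that the documents do not support:

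- *That the denominator is undefined.* Sections 3 and 7 and Table 7 place IFA and calcium in pregnant women. The 800 in Table 2 heads a block that also holds early initiation of breastfeeding, and the 1600 clients equal 4 × 400 in Table 4. What remains is the power question in step 1.
- *That ANCOVA leaves a stable difference untouched.* This is nearly so at ICC 0.001 but not at larger ICCs, and it rests on an assumed baseline term. Under change over time a stable difference cancels.
- *That a large share of women will have delivered.* The three-month lag belongs to the baseline round, which is already past.
- *That gestational age is not collected.* The questionnaires are not among the documents, so this cannot be judged. The gap is in pre-specification.

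It can also be said that section 10 names no covariates for any outcome, so this is a generic omission. But for a cumulative count in an ongoing pregnancy, gestation is a dominant determinant, so naming it is a better method and not just added detail. Table 7, module 9 intends the same tools for comparability; that does not rule out one added item.

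**Conclusion.** The point holds for three secondary outcomes: 100+ IFA, the mean IFA count and the mean calcium count. As planned, they depend strongly on gestation at interview, the arms are not randomised, and the stated model has no term for it. A gestational difference between arms could bias them in either direction, most clearly if it arises between rounds. That such a difference exists is not established, and a reader should not infer that the results will be biased.

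For scale, one week of difference is worth about 3 to 6 percentage points on 100+ IFA under the table's assumptions (0.7 to 5.1 under the alternative set), against a planned 9.5. The loss of precision does not depend on any imbalance. The power point is separate: about 0.76 instead of 0.80 if the denominator is the 400 pregnant women per group. Confidence is medium, and this is something that should be changed, not a fatal flaw.

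**What to change.** - In section 10, pre-specify gestational age at the intake interview, in a flexible form such as a spline, as a covariate in the models for 100+ IFA and the mean IFA and calcium counts among currently pregnant women. Record it at endline if it is not already recorded. Keep the model without it as a sensitivity analysis.
- Report women who have delivered by the home interview separately, so that ongoing and completed pregnancies are not mixed in one indicator.
- Report gestational age and the lag from facility visit to home interview by arm at endline, and at baseline where recorded. State what the ANCOVA baseline term is.
- Restate the power for 100+ IFA if its denominator is pregnant women only.

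**Cost.** At most one questionnaire item and a few sentences. The protocol is dated October 2021 and section 11 schedules the endline questionnaire for November 2021 to January 2022, so there was still time.

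**Downsides.** Gestational age is measured with error, so adjustment may be incomplete. Its functional form must be fixed in advance. It may not have been recorded at baseline, where fieldwork is over. Gestation at an ANC visit may itself be affected by an intervention that promotes visits, which is why the unadjusted model should be kept alongside.
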